7.1 Sample Size Determination

Sample Size Estimation and Power Analysis for the Primary Aim of the Study

Using a putative estimate of effect size ($d \sim 0.61$) as it relates to the Primary Aim, an *a priori* sample size estimation and power analysis was performed for the repeated measures design in the proposed study. The results suggest that a sample size of 25 participants per group ($N=120$) achieves 80% power, at a 0.05 alpha level (two-tailed), to detect standardized group mean differences (Cohen's d) as small as 0.61 in a 2-treatment by 2-biomarker status between-Participants group design with 6 (within-Participants) repeated measurements of the primary outcome (depression severity) having a compound symmetry covariance structure, when the assumed within-Participant correlation between observations (depression severity) on the same Participant is ≤ 0.50 (0.50 was based on guidance from our preliminary rTMS work). We anticipate some dropouts (~20% based on treatment discontinuation results from our previous rTMS studies). Thus, ~120 participants will be enrolled to allow for this expected rate of attrition with the intent of capturing a range of evaluable data for 100 participants. The Power Analysis and Sample Size (PASS) 2016 software, version 14.0.7, was used to carry out the sample size and power analysis.⁸⁹

We recognize that to definitively evaluate the relationship between rTMS Treatment (low frequency 1 Hz rTMS vs. high frequency 10 Hz rTMS) by biomarker status (high baseline ICF vs. low baseline ICF) on depression severity—since this relationship has not been previously studied, we have no previous findings to guide effect size selection for the present effort, and the current study would be the first of its kind to examine this effect in depressed youth—we will possibly need a larger sample size than the 100 participants put forth in this proposal. The selection of 100 participants was, in part, resource-driven. The sample size is designed, in part, to detect a moderate effect and to establish a *proof of concept* so as to expand to a subsequent, larger-scale multi-center study. Nevertheless, the current proposal will permit an evaluation of whether receiving low frequency (1 Hz) rTMS vs. high frequency (10 Hz) rTMS treatment according to patients' baseline biomarker status (ICF) shows initial evidence of a relationship with improvement in depression severity in a depressed adolescent population.

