| 
Statistical Methodology
 | 
For the primary aim, a linear mixed model analysis of repeated measures will be used to evaluate the repetitive transcranial magnetic stimulation (rTMS) by biomarker status interaction effect on depression severity (CDRS-R score) over 6 weeks of rTMS.
 
For the secondary aim, a within-participant linear mixed model analysis of repeated measures will be used to examine the change in ICF over 6 weeks of rTMS.
 
For the exploratory aims, a within-subjects linear mixed model analysis of repeated measures will be used to examine the change in cortical MRS measures of GABA, glutamate, and glutamine over 6 weeks of rTMS treatment in depressed adolescents. A multiple mediation/moderation path analytic model will be used to estimate the direct effect as well as the total and specific indirect effects of rTMS treatment on depression severity (at the 6-week endpoint) through each potential baseline moderator (anhedonia and adversity).
 |

1 Introduction

This document is a protocol for a human research study. This study will be carried out in accordance with the procedures described in this protocol, applicable United States government regulations and Mayo Clinic policies and procedures.

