2.1 Primary Objective

Aim 1 examines the relative efficacy of 6 weeks low frequency (1 Hz) or high frequency (10 Hz) left prefrontal rTMS according to a baseline ICF (**ICF-15 % MEP amp**) measure of glutamatergic tone in depressed adolescents. We will employ a biomarker stratified design. Depressed adolescents will be stratified by baseline ICF low (≤ 1.5) or ICF high (>1.5) groups prior to randomization.

- We expect that 6 weeks of 1 Hz rTMS will have greater efficacy (assessed by improvement in CDRS-R) in depressed adolescents with high baseline ICF compared to adolescents with low baseline ICF.
- We expect that 6 weeks of 10 Hz rTMS will have greater efficacy (assessed by improvement in CDRS-R) in depressed adolescents with low baseline ICF compared to adolescents with high baseline ICF.
- 6 weeks of 1 Hz rTMS will have greater efficacy (assessed by improvement in CDRS-R) than 6 weeks of 10 Hz rTMS in depressed adolescents with high baseline ICF.
- 6 weeks of 10 Hz rTMS will have greater efficacy (assessed by improvement in CDRS-R) than 6 weeks of 1 Hz rTMS in adolescents with low baseline ICF.

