7.2 Statistical Methods

Statistical Methods

All statistical analyses will be carried out using SAS software, version 9.4. The level of significance will be set at $\alpha = .05$ (two-tailed) and, to address multiple testing (where applicable), p-values will be adjusted using the False Discovery Rate.

Primary Aim

Data Analysis Plan for Primary Aim 1 (Hypotheses 1a–1d)

Primary Continuous Outcome: CDRS-R Total Score

Depression severity (measured by CDRS-R total) over the 6-week study period will be the primary continuous outcome measure. A linear mixed model analysis of repeated measures will be used to evaluate the rTMS Treatment (low frequency 1 Hz rTMS vs. high frequency 10 Hz rTMS) by biomarker status (high baseline ICF vs. low baseline ICF) interaction effect on depression severity (CDRS-R total) over 6 weeks of rTMS in depressed adolescents. The model will contain fixed effects terms for rTMS treatment, biomarker status, time, rTMS treatment \times biomarker status interaction, and baseline CDRS-R total score as a covariate. We will consider the inclusion of pubertal state and treatment resistance (as defined by Antidepressant Treatment History Form [ATHF] score) during the study period as additional covariates in the mixed model. Restricted maximum likelihood estimation, Type 3 tests of fixed effects, and generalized least squares will be used, with the Kenward-Roger correction applied to the appropriate and best fitting covariance structure. The sandwich (robust covariance matrix) estimator will also be considered. Least squares (LS) means will be estimated as part of the mixed model. Tests of Simple Effects will be examined so as to partition the interaction LS means effects; i.e., simple group main effects of biomarker status at each level of rTMS treatment (Hypotheses 1a, 1b) and simple group main effects of rTMS treatment at each level of biomarker status (Hypotheses 1c, 1d) will be examined. Cohen's *d* and Hedges' *g* will be calculated and interpreted as the effect size estimator for the between-Participants group main effects. A separate linear mixed model repeated measures analysis similar to that described above will also be implemented over 6 weeks of acute rTMS treatment and throughout the 6-month follow-up period. The PROC

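### The 80% power in Section 7.1 fits a comparison of two of the four cells, not the treatment-by-ICF interaction that the primary model tests, and four groups of 25 make 100, not 120

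*Combined protocol and SAP*

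**What the plan says.** Section 7.1 gives one power statement for the Primary Aim: "The results suggest that a sample size of 25 participants per group ($N=120$) achieves 80% power". Its inputs are two-sided alpha 0.05, Cohen's d of 0.61 between group means, a 2-treatment by 2-biomarker between-participant design, six repeated CDRS-R measurements, compound symmetry, and a within-participant correlation of at most 0.50 ("0.50 was based on guidance from our preliminary rTMS work"). On attrition it says "We anticipate some dropouts (~20% based on treatment discontinuation results from our previous rTMS studies") and plans to enrol about 120 so that about 100 are evaluable. Section 3.1 repeats the 120 and the 100. Section 7.1 also concedes that, for a definitive answer on treatment by biomarker status, "we will possibly need a larger sample size than the 100 participants put forth in this proposal".

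The test is described elsewhere. Section 7.2 says the mixed model evaluates the treatment by biomarker status "interaction effect on depression severity (CDRS-R total) over 6 weeks of rTMS in depressed adolescents", and the Statistical Methodology entry of the Study Summary likewise names the rTMS "by biomarker status interaction effect on depression severity (CDRS-R score) over 6 weeks of rTMS". Section 7.2 then adds: "Tests of Simple Effects will be examined so as to partition the interaction LS means effects". Those simple effects are Hypotheses 1a–1d, the four comparisons listed in Section 2.1. Each compares two of the four cells; the last, for example, is whether 10 Hz does better "than 6 weeks of 1 Hz rTMS in adolescents with low baseline ICF".

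**The concern.** The power figure and the primary test appear to concern different contrasts. A comparison of two cells uses half the participants and two means. The interaction uses all four means and is a difference of differences, so with equal cells its standard error is √2 times that of a two-cell comparison. A power worked out for one does not carry over to the other, and Section 7.1 does not say which was used.

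The sample size in the same sentence also does not add up: a 2 × 2 design has four groups, and four groups of 25 are not 120.

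What is at stake is how the result is read. If the interaction is not significant, readers need to know how large an interaction the trial could have found. Section 7.1 gives no interaction effect size, power or detectable difference.

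**Working it through.** **Inputs.** From Section 7.1: d = 0.61, m = 6 measurements, compound symmetry with ρ = 0.50, two-sided alpha 0.05 (z = 1.960), power 80% (z = 0.842), 25 per group, about 20% attrition, about 120 enrolled. From Section 5.3: an even split of high and low ICF is expected. Effects are in SD of a single CDRS-R measurement. Normal approximation, equal cells and no covariate unless stated.

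**1. Reproduce the plan's figure.** The variance factor of the six-visit mean is [1 + (m − 1)ρ]/m = (1 + 5 × 0.50)/6 = 0.5833.

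- Required n per group for two groups: 2 × (1.960 + 0.842)² × 0.5833 / 0.61² = 24.6, so 25.
- Standard error, 25 v 25: √(2 × 0.5833/25) = 0.2160. Power = Φ(0.61/0.2160 − 1.960) = 80.6%. A t test gives 79.0% (48 df) or 79.8% (96 df, pooled over four cells).

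The stated n and power are recovered as a contrast between two cells of 25, at unadjusted alpha.

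**2. Other readings of the same sentence.**

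| Contrast | SE | Power |
|---|---|---|
| Two cells, 25 v 25, effect 0.61 | 0.2160 | 80.6% |
| Two cells, 30 v 30 (120/4), effect 0.61 | √(2 × 0.5833/30) = 0.1972 | 87.1% |
| Treatment main effect, 50 v 50, effect 0.61 | √(2 × 0.5833/50) = 0.1528 | 97.9% |
| Interaction, 25 per cell, total contrast 0.61 | √(4 × 0.5833/25) = 0.3055 | 51.5% |
| Interaction, 25 per cell, +0.61 and −0.61 (total 1.22) | 0.3055 | 97.9% |

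The last row is the direction of the two treatment hypotheses, 1c and 1d, with 0.61 in each stratum. The ratio of the interaction SE to the two-cell SE is 0.3055/0.2160 = 1.41. In simulation (40,000 trials per setting, pooled t test on the six-visit mean), power was 79.8–79.9% for two cells, 50.5% for an interaction of 0.61 and 97.7% for 1.22.

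**3. Detectable interaction at 80% power.** 2.802 × 0.3055 = 0.856 SD, or about 0.43 per stratum in a symmetric crossover.

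**4. Sensitivity.** Section 7.1 allows a correlation below 0.50. The value 0.30, the 30/70 split and the baseline correlations below are assumptions used to show a range.

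| Setting | Two-cell power at 0.61 | Detectable interaction |
|---|---|---|
| 24 per cell, ρ = 0.50 | 79.0% | 0.874 SD |
| 25 per cell, ρ = 0.30 (factor 0.4167) | 91.6% | 0.723 SD |
| 30/70 ICF split of 100, ρ = 0.50 | 59.0% (15 v 15), 91.6% (35 v 35) | 2.802 × √[0.5833 × (2/15 + 2/35)] = 0.934 SD |
| Baseline covariate, r = 0.30 (factor 0.5833 − 0.30² = 0.493) | 86.7% | 0.787 SD |
| Baseline covariate, r = 0.50 (factor 0.5833 − 0.50² = 0.333) | 96.2% | 0.647 SD |

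Here r is the correlation between baseline and follow-up CDRS-R, which the plan does not give; both covariate rows use 25 per cell and ρ = 0.50. At 24 per cell, interaction power is 49.9% for a total contrast of 0.61 and 97.5% for 1.22.

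**5. Totals.** 4 × 25 = 100. 120 × (1 − 0.20) = 96, or 24 per cell. Keeping 100 after a 20% loss needs 100/0.80 = 125. Going from 120 to 100 is a loss of 20/120 = 16.7%.

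**The case against.** The simple effects are Hypotheses 1a–1d of the Primary Aim, so sizing the trial on them is legitimate. Section 7.1 speaks of group mean differences, which suggests a pairwise comparison, and it never claims interaction power. This stands as a defence of the choice of contrast. It does not supply the missing label or any interaction figure.

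No underpowering is shown. If 0.61 holds in opposite directions in the two strata, as the hypotheses predict, interaction power is 98%, better than the stated 80%. The planned baseline covariate would help further. This also stands. But the plan does not say that 0.61 is meant in each stratum, and on the other reading power is 51%.

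Section 7.1 already admits that more than 100 may be needed, that the number was partly set by resources and that the aim is proof of concept. That is a fair disclosure, but it has no number attached. The admitted lack of earlier findings on effect size is a reason to report a detectable contrast, which needs no assumed effect.

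The contrast is inferred from a matching number. An interaction scaled with coefficients of ±1/√2 has the same variance as a two-cell difference, so 0.61 on that scale would also give 80.6%. That is not a natural reading of a Cohen's d between group means, but it is why the PASS output should be checked before any relabelling.

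The 120 is explained shortly afterwards as enrolment, so nobody would size the trial wrongly. The 20% refers to treatment discontinuation. Section 4.4.1 asks discontinuers for the Week 6 assessments and Section 7.2 uses all available data, so some remain evaluable. Hence 24 per cell is the conservative case and the loss of power is small (80.6% to 79.0%). The power sentence still carries the wrong total.

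**Conclusion.** The point holds. The 80% matches one unadjusted simple-effect contrast between two cells of 25. It is not the power of the treatment-by-ICF interaction that the Study Summary and Section 7.2 make the primary model test, and no figure for that test is given. At 25 per cell, correlation 0.50, equal strata and no covariate, the detectable interaction is about 0.86 SD. Across the settings shown it ranges from 0.65 SD (covariate, assumed r = 0.50) to 0.93 SD (30/70 split). Which contrast PASS was given is an inference, though a strong one, since the other natural readings give 51%, 87% or 98%. Nothing here shows that the interaction is underpowered. The N of 120 contradicts the four groups of 25 in the same sentence, and 20% attrition from 120 leaves 96 rather than 100. This should be fixed, but it is a matter of reporting and does not affect the validity of the design.

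**What to change.** Reword Section 7.1 only.

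1. Check the PASS output. If it confirms the two-cell contrast, label the 80% as the power for one simple-effect comparison (Hypotheses 1a–1d) between two cells of 25, at within-participant correlation 0.50, without baseline or multiplicity adjustment, and about 79% at 24 per cell by normal approximation. If it shows another contrast, name that one.
2. Add a sentence such as:

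> With 25 per cell, equal cells, within-participant correlation 0.50 and no baseline covariate, the smallest treatment-by-ICF interaction contrast detectable with 80% power is about 0.86 SD. It is smaller at a lower correlation (0.72 SD at 0.30) or with the baseline covariate, and larger if the ICF strata are unequal (0.93 SD for a 30/70 split).

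   The sponsor may add the covariate range of 0.79 to 0.65 SD, marked as resting on assumed baseline correlations of 0.30 to 0.50. No interaction effect has to be assumed.
3. Replace the sample size in the power sentence with 25 per cell, 100 in total. State that about 120 enrolled gives about 96 completers at 20% attrition, and that partial data from discontinuers also enter the mixed model.

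The cost is a few sentences. There are no extra patients, no change to the analysis and no interaction effect to defend. The printed figures become slightly less favourable: 79% at 24 per cell, and 96 completers where the text now aims for 100 evaluable.

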Research participants: We will enroll participants ages 12 to 18 with the capacity to provide informed assent and parents (for participants younger than age 18) with the capacity to provide informed consent. Capacity to consent will be assessed with comprehension assessments. We are budgeted to recruit 120 depressed adolescents over five years for a target of 100 evaluable subjects (120 accounts for attrition based on our prior experience). We are budgeted to recruit 30 healthy adolescent participants for MRS comparison and test-retest studies. These goals are realistic given our group's experience with therapeutic rTMS and biomarker studies. Screening will include systematic safety assessments for safety to undergo both rTMS and ultra-high field (7 T) MRI/MRS.

Participants who fail to receive clinical benefit from Phase I (defined as a CDRS-R score of 40 or greater at post-treatment) will be offered enrollment in Phase II (N=50 max). The decision to enroll in Phase II can be made by the subject no more than 2 months after the last day of Taper Week 3. During phase II, participants will be assigned to 2 weeks of cTBS if their intracortical facilitation measure (baseline assessment for TBS extension trial) is >1.5 (building on the current speculation that cTBS would be expected to decrease cortical excitability and ICF measures). Participants will be assigned to 2 weeks of iTBS if their ICF (baseline assessment for TBS extension trial) is ≤ 1.5 (building on current speculation that iTBS would increase cortical excitability and ICF measures). All participants in Phase II will have a six month follow-up visit with depression severity measures (CDRS-R and BDI-II) and neurocognitive assessments.

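### Section 7.1 multiplies by 1.20 for dropout: 120 enrolled less 20% leaves about 96 evaluable (24 per cell), not the stated 100 (25 per cell)

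*Combined protocol and SAP*

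**What the plan says.** Section 7.1 gives the power statement as "a sample size of 25 participants per group ($N=120$) achieves 80% power". The test is two-sided at 0.05 and the effect sought is a Cohen's d of 0.61. Two treatments crossed with two levels of the biomarker make four cells, and the calculation is for a design "with 6 (within-Participants) repeated measurements of the primary outcome (depression severity) having a compound symmetry covariance structure". The correlation within a participant is taken as no more than 0.50.

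The allowance for loss follows: "We anticipate some dropouts (~20% based on treatment discontinuation results from our previous rTMS studies"). From this the section concludes that about "120 participants will be enrolled to allow for this expected rate of attrition", and it names 100 as the number meant to be evaluable.

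Section 3.1 repeats the pair of numbers: "We are budgeted to recruit 120 depressed adolescents over five years for a target of 100 evaluable subjects". It attributes the difference to attrition seen in earlier work, but gives no dropout rate and no power.

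Two other places bear on the point. Section 4.4.1 says that withdrawn participants are not replaced, whatever the reason. It also asks those who stop early to complete the Week 6 assessments within two days of their last session. Section 7.2 says that the primary mixed model uses all available data from the efficacy analysis set.

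**The concern.** Section 7.1 presents 120 as the consequence of a 20% dropout rate and a target of 100. The three numbers do not fit together. If two of them are kept, the third must change, and without replacement of withdrawals nothing later in the plan closes the gap.

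The parenthesis N=120 beside 25 per group adds to the difficulty. Four groups of 25 are 100, while 120 would be 30 per group. The enrolled number therefore stands where the evaluable number belongs, in the sentence that carries the power claim. A reader who wants to know how many evaluable participants the plan expects, and what the 80% refers to, has to redo the arithmetic. What is at stake is a correctly stated evaluable number. The loss of power is small, as shown below.

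**Working it through.** **Inputs.** From Section 7.1: two-sided alpha 0.05, d = 0.61 (SD = 1), 6 measurements, compound symmetry, correlation 0.50 (the top of the stated range), four cells, 25 per cell, about 20% dropout, about 120 enrolled. Equal cells are assumed. Section 5.3 expects an even split of high and low ICF, but no allocation ratio is stated, so 1:1 is my assumption.

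**Step 1: reproduce the plan's 25 per group.** Take the difference between two cells in the mean of 6 measurements.

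- Variance factor: (1 + 5 × 0.50)/6 = 3.5/6, so the effective SD is 0.764.
- Standard error of the difference: √(2 × (3.5/6)/n) = √(7/(6n)).
- Required n: 2 × [0.764 × (1.960 + 0.842)/0.61]² = 24.6, which rounds up to 25.
- At n = 25: 0.61/√(7/150) = 2.824, giving power of 80.6%.

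The stated 25 per group and 80% are reproduced, for a pairwise difference between two of the four cells.

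**Step 2: the dropout step.**

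- Evaluable from 120 at 20% loss: 120 × 0.80 = 96, or 24 per cell.
- Enrolment that leaves 100 at 20% loss: 100/0.80 = 125.
- Attrition at which 120 leaves 100: 1 − 100/120 = 16.7%.
- The plan's figure: 100 × 1.20 = 120.

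**Step 3: what 24 per cell does to power, counting completers only.** At n = 24, 0.61/√(7/144) = 2.767.

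| Calculation | 25 per cell | 24 per cell |
|---|---|---|
| Power, normal approximation | 80.6% | 79.0% |
| Power, t with 4n − 4 df | 79.8% | 78.2% |
| Power, t with 2n − 2 df | 79.0% | 77.3% |
| d detectable at 80% power, 2.8016 × √(7/(6n)) | 0.605 | 0.618 |

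The loss is 1.6 to 1.7 percentage points by each formula.

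**Step 4: sensitivity.**

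- *Partial data.* With 30 enrolled and 24 completing per cell, 6 drop out. Suppose each supplies k of the 6 measurements. The information per cell is then 24/(3.5/6) + 6k/(1 + 0.5(k − 1)). Over an assumed range of k = 1 to 5, power is 84% to 87%.
- *Lower correlation.* At 0.40 (assumed, within the stated range), 24 completers per cell give 84.8%.
- *Lower dropout.* At 18%, 98.4 remain and power is 80.0%. The count is still below 100.

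**The case against.** The strongest reply is that nothing of substance is lost. A reader might infer from the shortfall that the trial fails to deliver its 80% power. The documents do not support that reading, for three reasons.

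- On the formula that reproduces 25 per group, 24 per cell gives 79.0%. By the t formula with 4n − 4 df, the plan's own 25 already gives 79.8%.
- The 79.0% treats dropouts as contributing nothing. The 20% is a rate of stopping treatment, which is not the same as having no data. CDRS-R is scheduled weekly in Table 3, early discontinuers are asked for Week 6 procedures, and the mixed model uses what is available. Power under the planned analysis could exceed 80%.
- The correlation of 0.50 is the unfavourable end of the stated range.

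All of this stands as regards power. It does not repair the count. Section 7.1 itself separates enrolled from evaluable; if dropouts counted as evaluable, no step from 100 to 120 would be needed. The efficacy analysis set is not defined in the text available, so partial completers cannot simply be assumed to make up the difference.

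A second reply is that 20% and 120 are both marked as approximate. That softens the point, but 100 of 120 needs attrition of 16.7% or less, and even 18% falls short.

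A third is that Section 7.1 calls the sample partly resource-driven, describes the study as proof of concept and admits that a larger sample may be needed. This explains the choice of 100. It does not make 120 less 20% equal 100.

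A reader might also take Section 3.1 to be wrong on its own terms. It is not. It states neither a rate nor a power, and conflicts with the arithmetic only when read beside the 20% in Section 7.1.

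**Conclusion.** The evaluable count in Section 7.1 is wrong on the plan's own inputs. At 20% attrition, 120 enrolled gives about 96 evaluable (24 per cell), four short of 100 in total and one short per cell. The label N=120 beside 25 per group is also wrong: it should be 100. Both conclusions are arithmetic and rest only on equal cells and on dropouts being non-evaluable, as Section 7.1 treats them.

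The consequence for power is minor: about 1.6 points, from 80.6% to 79.0% by the normal approximation (about 78% by t with 4n − 4 df), for a pairwise difference between two cells, counting completers only. The figure may be higher once partial data enter the model. It says nothing about power for the treatment-by-biomarker interaction that Section 7.2 sets out to evaluate, which is a separate question. This is a correction to the text; it is no reason to change the design.

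**What to change.** In Section 7.1:

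- Replace N=120 beside 25 per group with N=100 evaluable.
- Replace the attrition sentence with wording such as: *With 120 enrolled and 20% attrition, about 96 participants (24 per cell) are expected to complete; 100 would be reached only if attrition is at most 16.7%.*
- If power is restated, name the contrast and the basis: *about 79% (normal approximation; about 78% by t) for a pairwise difference of d = 0.61 between two of the four cells, counting completers only; partial data from dropouts in the mixed model may raise this.*
- If partial completers are meant to count as evaluable, say so and define the term.

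In Section 3.1, align the evaluable target with the restated count. No power statement is needed there.

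The cost is a few sentences and a slightly less favourable evaluable number. No extra enrolment, design change or change in analysis is asked for.
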